6. STUDY DURATION / TIMELINE

The study will have a total duration of 70 days per enrolled patient. Please refer to the attached Gantt chart.

Study Start: 09/2022 Recruitment Closure: 12/2022 Study End: 07/2023

7. STATISTICAL ANALYSIS

7.1 Sample Size

Assuming a placebo effect of 30% reduction in the primary outcome (fatigue assessed by Chalder Fatigue Scale - Likert 0-33), a statistical power of 80% with a significance level of 0.05 (two-tailed),

we estimate that 42 patients per arm are needed to detect a 60% efficacy of the probiotic in reducing the same parameter. This reduction, if confirmed, would have significant clinical relevance, indicating a substantial efficacy compared to placebo. Considering a dropout rate of 15%, we believe that recruiting 48 actual patients per arm is necessary to demonstrate this efficacy.

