2. STUDY OBJECTIVE/HYPOTHESIS

2.1 Primary Objectives

The primary objective of this study is to test whether a high-concentration probiotic formulation (e.g., VSL#3®) can reduce the degree of clinically significant fatigue in ambulatory patients suffering from Long-Covid-19 Syndrome, i.e., the persistence of systemic symptoms 4 weeks after molecular detection of SARS-CoV-2

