4. PROCEDURES RELATED TO THE STUDY

4.1 Intervention Patients

Patients will be referred by the Pneumology and Infectious Diseases outpatient clinics for a preliminary evaluation of inclusion and exclusion criteria, within the context of scheduled visits for sequelae of SARS-CoV-2 infection. The recruitment phase is divided into an initial screening visit (Visit 1, t-2) to determine if the patient meets the inclusion/exclusion criteria. Following this visit, a

14-day run-in period will be conducted to screen for non-adherent patients, i.e., those who do not show up for the subsequent visit. The patient will return for a visit at 14 days (Visit 2, t0) when randomization will occur, and the patient will be assigned to the treatment or placebo group. The patient will be instructed to take the treatment (supplement or placebo) at the prescribed dosage of two sachets per day for a consecutive and continuous period of four weeks. During this visit, all immunological and microbiological analyses will be performed, including the collection of 20 mL of blood and 1 g of fecal material. The patient will also complete clinical questionnaires to assess the primary and secondary endpoints. The clinical questionnaires will be stored in a deidentified form at the Gastroenterology and Endoscopy Unit, while the biological samples will be shipped and analyzed at the Mucosal Immunology Laboratory of the IEO. Considering the short duration of the study and the lack of literature data demonstrating a clear benefit of VSL#3 on this syndrome, no crossover between study arms is planned under any circumstances. During the study, the use of immunosuppressants or immunomodulators, glucocorticoids, opioids, antidepressants, or anxiolytics at regular and continuous dosages is not allowed. If there is a clinical necessity for antibiotic therapy, it will result in discontinuation of the study. After completing the 28-day treatment period, the patient will return for a visit (Visit 3, t4) where immunological and microbiological analyses will be repeated, and questionnaires will be completed again to evaluate the primary and secondary endpoints. An additional visit with completion of clinical questionnaires will be scheduled 28 days after the end of the treatment (Visit 4, t8) to assess whether any response is maintained at the end of the treatment period.

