5. ENDPOINTS

5.1 Primary Endpoint

Demonstration of a statistically significant difference between the placebo group and the treatment group in the scores of the Chalder Fatigue Scale at the end of the treatment period (t4). The Chalder Fatigue Scale is a validated scale used to assess fatigue in the context of CFS/ME [39-41].

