7.2 Data Analysis

Both intention-to-treat and per-protocol analyses will be conducted. Depending on the distribution of the data, Student's t-test or Wilcoxon Mann-Whitney test will be used for continuous variables, and Chi-square test or Fisher's exact test for categorical variables. Relationships between multiple variables will be assessed using linear or logistic regression tests based on the nature of the available data. Statistical analysis will be performed using the RStudio software (R Core Team, 2020) and Stata software (StataCorp, 2013). No interim analyses are planned due to the short duration of the study and the relatively small number of enrolled patients.

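### The 42 per arm in Section 7.1 matches a comparison of two proportions (30% v 60%, inferred), but the primary endpoint is a mean score with no SD given; 48 per arm also falls short of 42 after 15% dropout

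*Combined protocol and SAP*

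**What the plan says.** Section 7.1 (Sample Size) opens: "Assuming a placebo effect of 30% reduction in the primary outcome (fatigue assessed by Chalder Fatigue Scale - Likert 0-33". It sets 80% power and a two-tailed 0.05 level, and then says "we estimate that 42 patients per arm are needed to detect a 60% efficacy of the probiotic in reducing the same parameter". It goes on: "Considering a dropout rate of 15%, we believe that recruiting 48 actual patients per arm is necessary". Section 4.2 carries the resulting total of 96, allocated 1:1.

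The other sections describe a comparison of scores. Section 2.1 asks whether the probiotic "can reduce the degree of clinically significant fatigue in ambulatory patients". Section 5.1 defines the primary endpoint as a difference between groups "in the scores of the Chalder Fatigue Scale at the end of the treatment period (t4"; it names no scoring mode, and the 0-33 Likert form comes from Section 7.1. In Section 7.2 the "t-test or Wilcoxon Mann-Whitney test will be used for continuous variables", while the chi-square or Fisher's "exact test for categorical variables".

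No SD, baseline mean or standardised effect for the Chalder score appears anywhere, and no sample-size formula is named. Section 4.1 schedules the last visit "to assess whether any response is maintained at the end of the treatment period", and Section 5.2 relates the microbiota measures to clinical response on fatigue, but no response threshold is set. The only Chalder cut-off, a dichotomous score of 4 or more in Section 3.2, is an entry criterion.

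**The concern.** Two percentages with a power and a significance level are enough to size a comparison of two proportions. They are not enough to size a comparison of two mean scores, which also needs the spread of the scores and the level they start from. Section 7.1 gives only the percentages, attaches them to a 0-33 score, and still arrives at a definite 42 per arm.

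At stake is the stated power of the primary analysis. A reader cannot tell what difference in fatigue points the trial was sized to detect, or whether 96 patients are enough for the sponsor's own 30% v 60% target on the endpoint that will be tested.

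The dropout step raises a smaller question: whether 48 recruited per arm leaves the 42 that the same paragraph says are needed.

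**Working it through.** **Inputs from the plan.** Two-sided alpha 0.05 (z = 1.96), power 80% (z = 0.8416), 30% and 60%, 42 per arm, 15% dropout and 48 per arm (all Section 7.1); 1:1 allocation and n = 96 (Section 4.2).

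**1. Reproducing 42.** Treat 30% and 60% as proportions of patients, with mean proportion 0.45. The pooled formula gives

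n = [1.96 × √(2 × 0.45 × 0.55) + 0.8416 × √(0.3 × 0.7 + 0.6 × 0.4)]² / 0.3² = (1.379 + 0.565)² / 0.09 = 41.97, that is 42 per arm.

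Power by the same formula at n = 42 is 80.0%. Variants give 39.2 (unpooled), 41.8 (arcsine), 43.2 (pooled variance in both terms) and 49 (continuity-corrected).

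**2. What the planned test can detect.** For a two-sample t-test at two-sided 0.05 and 80% power (noncentral t), the detectable difference is 0.619 SD at 42 per arm, 0.626 SD at 41 and 0.634 SD at 40. Turning this into points needs an SD, which the documents do not give. For assumed SDs, equal in both arms, at 40 per arm:

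- SD 5: 0.634 × 5 = 3.2 points
- SD 8: 0.634 × 8 = 5.1 points
- SD 10: 0.634 × 10 = 6.3 points

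**3. Would 40 per arm meet the 30% v 60% target?** If the percentages are mean reductions from a common baseline mean B, the t4 means are 0.7B and 0.4B, and the difference is 0.3B. The baselines and SDs below are assumptions. The cells are t-test power at 40 evaluable per arm.

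| Assumed baseline (difference) | SD 5 | SD 8 | SD 10 |
|---|---|---|---|
| 15 (4.5 points) | 98% | 70% | 51% |
| 20 (6.0 points) | >99% | 91% | 75.5% |
| 25 (7.5 points) | >99% | 98.5% | 91% |

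Six of the nine cases exceed 90% and three fall below 80%. Over the same grid, the number needed per arm for 80% power runs from 7 (baseline 25, SD 5) to 78 (baseline 15, SD 10).

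**4. Dropout.** 48 × 0.85 = 40.8 evaluable per arm, below 42. Keeping 42 needs 42 / 0.85 = 49.4, that is 50 per arm. Starting from 48, 42 remain only if dropout is at most 1 − 42/48 = 12.5%. The stated 48 is probably 42 × 1.15 = 48.3 (inferred). The effect on power for 30% v 60% as proportions is:

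| Evaluable per arm | Pooled formula | Uncorrected chi-square, exact enumeration | Fisher's exact test, exact enumeration |
|---|---|---|---|
| 40 | 78.0% | 79.6% | 72.5% |
| 41 | 79.0% | 81.3% | 74.5% |
| 42 | 80.0% | 82.8% | 76.4% |

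**The case against.** The strongest reply is that the two-proportion origin is an inference. Section 7.1 names no formula, and its wording reads naturally as mean reductions in a score, which agrees with Sections 2.1, 5.1 and 7.2. A t-test at 0.62 SD also needs 42 per arm; a 6-point difference with an SD of about 9.7 would do it. On this view the plan does not contradict itself: it omits inputs, and several of the cases worked above show ample power. The mentions of response in Sections 4.1 and 5.2 may be ordinary wording rather than signs of a responder endpoint.

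Much of this is fair. The origin of 42 is inferred, inadequate power is not shown, and the mentions of response do not prove that a responder analysis was intended. But the main point does not depend on the origin. On the mean-reduction reading, an SD and a baseline mean are indispensable, and neither is given. On the responder reading, the calculation works but the endpoint and test do not match it. Neither reading supports 80% power for the primary comparison as the plan is written.

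On dropout, the reply is that multiplying by 1.15 is a common shortcut, that the loss of power is trivial, and that an intention-to-treat analysis might retain some dropouts. The first two points confirm that the slip is minor. The third cannot be relied on, because Section 7.2 gives no method for missing t4 scores.

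**Conclusion.** The concern holds and should be fixed. The stated 80% power is unsupported for the planned comparison of t4 Likert scores, because the plan gives no SD, baseline mean or standardised effect. It is not shown to be false. Depending on the SD and baseline, 42 per arm may be more or fewer than needed.

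What can be said without further inputs is that about 40 evaluable per arm gives 80% power for a difference of 0.63 SD by t-test. This assumes equal SDs, no t4 score from dropouts, and the t-test rather than the Mann-Whitney alternative that Section 7.2 also allows. The conversion to points, and any power for the 30% v 60% target, rest on assumed values.

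The dropout shortfall is real but small: 40.8 against 42 evaluable per arm, costing about 1 to 2 percentage points of power by the formula that reproduces 42. It would not by itself justify changing the sample size.

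**What to change.** Keep 48 per arm and n = 96, and restate Section 7.1 along these lines: 48 randomised per arm, about 40 evaluable after 15% dropout, giving 80% power at two-sided 0.05 for a between-arm difference of 0.63 SD in the t4 Chalder Likert score by t-test.

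That sentence describes what the chosen number can detect; it does not justify the target. So add the assumed SD and baseline mean with their source, convert 0.63 SD to points, and set the result against the 30% v 60% target. State whether 30% and 60% are mean reductions.

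If they are proportions of responders, define the response (which would also settle the wording in Sections 4.1 and 5.2), label the comparison a secondary responder analysis, and name its test. Give the power that belongs to that test and say how it was calculated: at 40 to 41 per arm, 78% to 79% by the pooled formula (80% to 81% for the uncorrected chi-square test by exact enumeration), or 72.5% to 74.5% for Fisher's exact test.

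The cost is a rewritten paragraph and a search for a sourced SD and baseline mean. No extra patients are needed and Section 4.2 is unchanged. The drawback for the sponsor is that the power for its own target may turn out less favourable than 80%.

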4.2 Randomization

Randomization will be managed using the REDCap (Research Electronic Data Capture) software. Considering the relatively small number of anticipated patients (n = 96, see dedicated section), we have planned a permuted block randomization with a 1:1 ratio between the placebo and treatment groups. Given the higher expression of the Long-Covid-19 Syndrome in females, randomization will be stratified by sex. We do not anticipate any socio-health or ethical factors that could interfere

with the randomization process to bias patients into one arm over another.

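### The 15% dropout allowance falls short: 48 per arm leaves 40.8 evaluable, below the 42 that the plan says it needs for 80% power

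*Combined protocol and SAP*

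**What the plan says.** Section 7.1 (Sample Size) sets a two-sided significance level of 0.05 and 80% power. It assumes a 30% reduction in fatigue on placebo and 60% on the probiotic, and concludes: "we estimate that 42 patients per arm are needed". The next step adds the allowance for losses: "Considering a dropout rate of 15%, we believe that recruiting 48 actual patients per arm is necessary to demonstrate this efficacy".

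Section 4.2 (Randomization) carries the result forward as a total of 96 patients, allocated 1:1. The protocol does not say which formula takes 42 to 48, and no other section revisits the figure.

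Three further places matter for the interpretation. Section 5.1 defines the primary endpoint as a between-group difference in Chalder Fatigue Scale scores at t4. Section 7.2 plans both intention-to-treat and per-protocol analyses and names no method for missing data. Section 4.1 places randomization after a 14-day run-in.

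**The concern.** A dropout rate is a fraction of the patients who enter the trial. To finish with a required number, one divides that number by one minus the rate. Multiplying by one plus the rate gives too few, because the loss then falls on the enlarged group as well.

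The figure of 48 looks like the second calculation. If so, the trial would be expected to end with fewer evaluable patients than its own power statement requires, under its own dropout assumption. The only purpose of the allowance is to protect the 42, and here it does not do so.

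What is at stake is the accuracy of the sample-size statement: a reader would take 96 patients to give 80% power after 15% dropout, when they give slightly less.

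**Working it through.** **Inputs, all from section 7.1 unless noted**

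- Two-sided alpha 0.05; power 80%
- Placebo 30%, probiotic 60%
- Needed per arm: 42
- Dropout: 15%
- Recruited per arm: 48 (total 96, 1:1, section 4.2)

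**Step 1. Reproduce the plan's 42.** The plan names no formula. Treating 30% and 60% as proportions of responders (an assumption), the pooled two-proportion formula without continuity correction is

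n = [z(0.975) x sqrt(2 x p̄ x (1 − p̄)) + z(0.80) x sqrt(p1(1 − p1) + p2(1 − p2))]² / (p2 − p1)²

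With p1 = 0.30, p2 = 0.60 and p̄ = 0.45:

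n = [1.960 x sqrt(0.495) + 0.842 x sqrt(0.45)]² / 0.09 = 41.97, so 42 per arm.

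This matches the stated figure. There is almost no slack from rounding (41.97 to 42).

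**Step 2. Reproduce the plan's 48.** 42 x 1.15 = 48.3, which rounds down to 48. This is the likely origin, inferred from the match. The steps below do not depend on it.

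**Step 3. Apply the stated dropout to the stated recruitment.**

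- Per arm: 48 x 0.85 = 40.8, against 42 needed
- Both arms: 96 x 0.85 = 81.6, against 84 needed

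**Step 4. Find the dropout that 48 does cover.** 1 − 42/48 = 0.125, or 12.5%.

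**Step 5. Find the number that covers 15%.** 42 / 0.85 = 49.4, so 50 per arm and 100 in total. Check: 50 x 0.85 = 42.5, which is enough. Note that 49 x 0.85 = 41.65, which is not.

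**Step 6. Power at the number that remains.** Solving the step 1 formula for power, with n per arm:

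power = Φ{[0.30 x sqrt(n) − 1.960 x sqrt(0.495)] / sqrt(0.45)}

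At n = 40.8: [1.916 − 1.379] / 0.671 = 0.801, and Φ(0.801) = 78.8%.

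| Evaluable per arm | Power, 30% vs 60% |
|---|---|
| 42 | 80.0% |
| 41 | 79.0% |
| 40.8 | 78.8% |
| 40 | 78.0% |

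**Step 7. Does the size of the loss depend on the proportions reading?** Take a two-sample t-test and choose the standardised difference so that 42 per arm gives exactly 80% power. That difference is 0.6186; it is back-calculated and does not appear in the protocol. At 40.8 per arm the power is again 78.8%. This is not independent support for the 80%. It shows only that, if 42 gives 80%, the drop to 40.8 costs about 1.2 points under either type of test.

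**The case against.** The strongest reply is that the discrepancy is trivial: 1.2 patients per arm and 1.2 points of power, with no effect on design, conduct or conclusions. Part of the gap between 96 and 100 is also rounding, since 84 / 0.85 = 98.8 before each arm is rounded up. All of that is true, and it limits the weight of the point. It does not make the sentence correct: 42, 15% and 48 stand in one paragraph and do not fit together.

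A second reply is that an intention-to-treat analysis would keep all 48 per arm, so 40.8 would not be the analysed number. The shortfall does apply to patients with a t4 score. But section 7.2 gives no missing-data method, and a patient with no t4 score contributes nothing to a t-test or Mann-Whitney test unless a value is imputed. By inflating for dropout at all, section 7.1 treats dropouts as not counting towards 42.

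A third is that the run-in removes unreliable patients beforehand. The allowance is stated per arm, however, and arms exist only after randomization, which follows the run-in. If 48 were instead counted before the run-in, the number left would be no larger.

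A fourth has real substance. The 42 reproduces only if 30% and 60% are read as responder proportions, while the endpoint is a score and section 7.1 gives neither a standard deviation nor a responder definition. Any absolute power figure, whether 80% or 79%, is therefore conditional on accepting the 42. That is a separate weakness of the sample-size section. The headcount shortfall in steps 3 to 5 needs only 42, 15% and 48.

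**Conclusion.** The point holds. At the stated 15% dropout, 48 per arm leaves 40.8 evaluable patients where the plan requires 42, so 96 patients do not deliver the stated 80% power. The shortfall is 2 patients per arm at recruitment (48 against 50; 96 against 100 in total) and about 1.2 percentage points of power (78.8% against 80.0%).

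The headcount result assumes only that dropout is a fraction of those randomized and that dropouts do not count towards the 42. The power result assumes in addition that 42 per arm does give 80%. The multiplication by 1.15 is an inference about how the error arose, and nothing rests on it.

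This is a definite error with a small effect. It should be corrected, but it does not threaten the trial.

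**What to change.** Keep 96 patients and correct the dropout sentence in section 7.1 in one of two ways:

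- State that 48 per arm allows for 12.5% dropout, leaving 42 evaluable per arm and 80% power. The protocol offers no support for 12.5% in place of 15%, so this option should be used only if the investigators consider that rate realistic.
- Keep 15% dropout and state that 48 per arm leaves about 41 evaluable per arm and about 79% power. This leaves the stated assumption untouched and is the more direct correction.

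In either case, say that the power figure is conditional on the calculation behind 42, and name the formula used. The total of 96 in section 4.2 can stand.

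The cost is one sentence, with a slightly less favourable power or dropout figure and no extra patients. Holding both 80% power and 15% dropout would instead take 50 per arm, 4 more patients in total.

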7.2 Data Analysis

Both intention-to-treat and per-protocol analyses will be conducted. Depending on the distribution of the data, Student's t-test or Wilcoxon Mann-Whitney test will be used for continuous variables, and Chi-square test or Fisher's exact test for categorical variables. Relationships between multiple variables will be assessed using linear or logistic regression tests based on the nature of the available data. Statistical analysis will be performed using the RStudio software (R Core Team, 2020) and Stata software (StataCorp, 2013). No interim analyses are planned due to the short duration of the study and the relatively small number of enrolled patients.

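### The primary comparison of t4 Chalder scores ignores the t0 score and the sex stratum, both already collected, and so gives up precision

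*Combined protocol and SAP*

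**What the plan says.** Section 5.1 defines the primary endpoint as a difference between placebo and treatment in Chalder scores at t4, with no baseline term. Section 7.1 names the scoring: "fatigue assessed by Chalder Fatigue Scale - Likert 0-33".

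Section 7.2 is the whole analysis plan. For continuous outcomes: "Depending on the distribution of the data, Student's t-test or Wilcoxon Mann-Whitney test will be used for continuous variables". Its only reference to a model is: "Relationships between multiple variables will be assessed using linear or logistic regression tests". That sentence names no outcome, covariate or treatment effect.

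The covariates are already available. Section 4.1 says of the randomization visit (t0): "The patient will also complete clinical questionnaires to assess the primary and secondary endpoints". It says of the end-of-treatment visit (t4): "questionnaires will be completed again to evaluate the primary and secondary endpoints". Section 4.2 states that "randomization will be stratified by sex".

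**The concern.** A two-sample test of t4 scores leaves in the error term whatever part of the t4 variance the same patient's t0 score could explain. The same people answer the same questionnaire four weeks apart, so some correlation is a reasonable expectation, although the documents do not report one. In a trial of 96 patients that explained variance is worth recovering, because it buys a narrower interval for the treatment effect without recruiting anyone else.

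No bias is at stake. Randomization makes the unadjusted comparison unbiased, and its standard error already allows for chance baseline imbalance. Sex was made a stratification factor and then does not appear in the comparison; it should be in the model to match the design, not because it adds much power.

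**Working it through.** **The plan's own figure.** Section 7.1 gives 42 per arm for 30% against 60%, 80% power, two-sided 0.05. The pooled two-proportion formula reproduces it:

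n = [1.960·√(2·0.45·0.55) + 0.842·√(0.3·0.7 + 0.6·0.4)]² / 0.30² = 41.97, so 42 per arm.

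Then 42 × 1.15 = 48.3, the stated 48. Neither an SD nor a t0–t4 correlation enters this calculation, so both must be assumed below.

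**Evaluable patients.** 48 × 0.85 = 40.8, taken as 41 per arm (82 in total).

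**Effect of adjustment on the interval.** In large samples ANCOVA multiplies the standard error by √(1 − r²): 0.954, 0.866 and 0.800 for r of 0.3, 0.5 and 0.6. With 82 patients and a model containing treatment, t0 score and sex, estimating the coefficients has a cost, and the CI width ratio is

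[t(78)/t(80)] × √[(1 − r²)(1 + 1/77)].

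Setting this ratio to 1 gives a break-even r of about 0.12. A simulation agrees with the formula: 100,000 trials per setting, normal data, 65% women assumed, no sex effect. It also gives power under an assumed standardized effect d = 0.6186, the value at which a t-test with 42 per arm has 80% power.

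| Assumed r | Change in 95% CI width | Power, adjusted (unadjusted 78.9%) |
|---|---|---|
| 0 | +0.7% | 78.3% |
| 0.1 | +0.2% | 78.6% |
| 0.2 | −1.3% | 79.9% |
| 0.3 | −3.9% | 82.1% |
| 0.5 | −12.8% | 88.8% |
| 0.6 | −19.4% | 93.1% |

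Under the null, both methods rejected in 4.9% to 5.1% of trials.

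**In Likert points (SD assumed).** CI half-width, unadjusted, then adjusted at r = 0.3, 0.5, 0.6:

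- SD 4: 1.8, then 1.7, 1.5, 1.4
- SD 6: 2.6, then 2.5, 2.3, 2.1
- SD 8: 3.5, then 3.4, 3.1, 2.8

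**Sensitivity of power to the assumed effect.**

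- At d = 0.5, unadjusted power is 60.9%, against 64.5%, 72.6% and 79.3% adjusted at r = 0.3, 0.5 and 0.6.
- If 30% and 60% in section 7.1 are read as mean score reductions, d = 0.3 × baseline mean / SD. Over assumed means of 15, 20 and 25 and SDs of 4, 6 and 8, unadjusted power is at least 91.8% in eight of nine combinations. The ninth (mean 15, SD 8; d = 0.3 × 15/8 = 0.56) has 71% unadjusted, against 74%, 82% and 88% adjusted.

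**Sex alone.** With an assumed difference of 0.5 SD between the sexes, r = 0 and d = 0.6186, power goes from 77.3% unadjusted to 78.4% adjusted.

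**The case against.** The planned test is a legitimate analysis of a randomized endpoint, so this is an improvement and not an error. That stands.

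The benefit is not documented. Every r above is assumed, and entry requires a dichotomous Chalder score of at least 4, which may narrow the baseline range and lower r. As an illustration, if the t0 SD were cut to 60–80% of its unrestricted value, an r of 0.5 would become about 0.33–0.42 and the large-sample gain would fall from 13% to about 5–9%. This is a fair caution about size, but those values are still well above the break-even of 0.12. Eligibility is also judged 14 days before t0, which may soften the restriction.

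The power figures lean on d = 0.62, back-solved from a sample size that is also a two-proportion result. That stands too, and is why the interval width, which does not depend on d, should carry the argument.

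The calculations assume normal data, so they show a gain over the t-test only. In one strongly skewed case that was simulated, Mann-Whitney had more power than ANCOVA (about 91% against 82–89%). This limits the claim and is a reason to retain Mann-Whitney as a sensitivity analysis.

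Finally, the regression sentence in section 7.2 leaves room for an adjusted analysis. It permits one without prespecifying it, and an adjustment chosen after seeing the data would be a matter of analyst discretion.

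**Conclusion.** The point holds. The primary analysis as written is unadjusted, and the plan already collects what is needed to sharpen it. The cost of leaving it is precision only: relative to the t-test, at 41 per arm and approximately normal scores, an interval that could be about 4% to 19% narrower for r between 0.3 and 0.6. There is essentially no difference at r of 0.1 and a gain of about 1% at r of 0.2. Power rises materially only if the true effect is moderate (d around 0.5 to 0.6). If the effect is as large as most literal readings of section 7.1 imply, the benefit is mainly the narrower interval. The change should be made, but the trial is not invalid without it.

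**What to change.** In section 7.2, name as the primary analysis a linear model (ANCOVA) of the t4 Chalder Likert score (0–33) on treatment, t0 Chalder Likert score and sex, in the intention-to-treat population. Report the adjusted mean difference with its 95% CI. Keep Mann-Whitney and the per-protocol analysis as sensitivity analyses. Use the same baseline- and sex-adjusted form for the other questionnaire scores; the gain there has not been calculated.

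For the covariates this is a change of wording only, since the t0 score and sex are already collected. The figures above use 41 evaluable patients per arm, not the 48 randomized. How missing t4 scores enter the intention-to-treat analysis has to be settled whichever test is used. The worst-case statistical cost against the t-test, with r of 0 and sex not prognostic, is about 0.6 percentage points of power (78.9% to 78.3%) and an interval about 0.7% wider.
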